13.3. Efficacy Analyses

Best corrected visual acuity will be assessed independently for each eye and the worse value for each test lens set and subject will be selected for the primary analysis. Each subject's BCVA LogMAR score from the phoropter-based lenses will be subtracted from the BCVA LogMAR

Version 3.0 (17 June 2019)

score from the EyeQue VisionCheck-based lenses. The mean, SD, and two-sided 95% confidence interval (CI) will be reported across all subjects for worst eye, OD, OS, and OU, and if the upper bound (one sided 95% CI) does not include the value 0.1 for the worst eye comparison, then non-inferiority will be declared. This will be repeated using BCVA scores from the autorefractor-based lenses and EyeQue VisionCheck-based lenses.

Raw refraction values for the phoropter and VisionCheck will be plotted and Pearson correlations calculated. This will be repeated using autorefractor and EyeQue VisionCheck values.

Subject preference data will be tabulated with counts and percentages of subjects that considered the EyeQue VisionCheck trial lenses better as well as the counts and percentages of subjects that considered the EyeQue VisionCheck trial lenses better or equal.

Analyses will be repeated for each age stratum including ages 30 through 65 and ages 45 through 65.

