7.3. Study Endpoints

7.3.1. Efficacy Endpoints

Primary Endpoint:

• Statistical non-inferiority of EyeQue VisionCheck compared with phoropter assessed by BCVA (OD, OS, and OU) measured using trial lens frames that correct the refractive error measured by each device analyzed with age stratum 45 through 65 years.

Secondary Endpoints:

- Comparison of raw refraction values produced using the EyeQue VisionCheck and the phoropter analyzed with age strata 30 through 65 years and 45 through 65 years.
- Statistical non-inferiority of EyeQue VisionCheck compared with autorefractor assessed by BCVA (OD, OS, and OU) measured using trial lens frames that correct the refractive error measured by each device, analyzed with age strata 30 through 65 years and 45 through 65 years.
- Comparison of raw refraction values produced using the EyeQue VisionCheck and the autorefractor analyzed with age strata 30 through 65 and 45 through 65 years.
- Statistical non-inferiority of EyeQue VisionCheck compared with phoropter assessed by BCVA (OD, OS, and OU) measured using trial lens frames that correct the refractive error measured by each device analyzed with the age stratum 30 through 65 years.

Exploratory Endpoint:

• Subject preference of trial lens frames that correct the refractive error measured by each of the 3 devices: EyeQue VisionCheck, phoropter, and autorefractor

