7.4. Rationale for Study Design and Control Group

A clinical study based on statistical non-inferiority is the most appropriate means to assess the effectiveness and performance of the EyeQue VisionCheck device relative to the comparator devices, the phoropter and autorefractor, that are standard eye care diagnostic devices used to obtain refraction values.

Masking of the subjects and assessors to the refraction values used to prepare the 3 trial lens frames is appropriate to control and minimize bias in the assessment of BCVA as these LogMAR

scores will be used for determination of statistical non-inferiority. A statistical non-inferiority margin of 0.1 LogMAR has been chosen because the one-line ETDRS difference is an acceptable boundary for corrected visual acuity, with larger differences likely to be unacceptable to patients and smaller differences difficult to reliably detect and/or reproduce.

Based on the intended use for obtaining refraction values, a one-day evaluation is appropriate because standard-of-care eye exams in which refraction values are obtained are typically repeated on a periodic basis, such as yearly, and it is not anticipated that refraction values would change over a short duration where additional repeated measurements would be necessary for this study. Visual acuity may fluctuate often; however, there is no appreciable change over a period of a several months.

The design allows for enrollment of subjects 30 to 65 years because subjects younger than 30 years of age are more likely to have visual accommodation that would add complexity to this comparative study. Younger subjects may be assessed in a separate clinical study.

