13. STATISTICS

13.1. Power and Sample Size Determination

Approximately 200 subjects will be enrolled in this study to achieve a minimum of 100 evaluable subjects to assess the effectiveness and safety of the EyeQue VisionCheck. The initial cohort included 39 subjects; therefore, approximately 160 additional subjects will be enrolled in the study. Based on prior study data, rejection of non-inferiority bounds of 0.1 LogMAR (one line) and 0.05 LogMAR (one-half line) would require approximately 10 and 40 subjects, respectively, with 90% power on the BCVA from the resulting lens from each approach. This assumes the devices are roughly equivalent and the standard deviation (SD) is 0.077; these data are based on a previous version of the EyeQue VisionCheck device tested against an autorefractor. The proposed sample size has been inflated to allow for the possibility that a larger standard deviation will be observed in the current study, as well as to allow for comparisons within each stratum. A software error in the EyeOue app was identified and the algorithm for the EyeQue app was updated with more stringent parameters which may also impact the number of evaluable subjects. Due to the updates to the parameters, there may be additional subjects for which EyeQue VisionCheck refraction values are not produced, leading to an increase in the number of subjects that will not be evaluated for the primary endpoint. Of the approximately 160 additional subjects that will be enrolled in the study, it is anticipated that approximately 60 subjects will not be evaluable due to failing screening or not having refraction values produced with the EyeQue VisionCheck. Additionally, the larger sample size provides a sufficiently robust database for investigations of the secondary outcomes and descriptions of the EveQue VisionCheck's performance characteristics.

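### Non-inferiority is decided on a one-sided 95% bound that the plan does not list for reporting, and the same rule serves one primary and three secondary claims with no testing order

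*Combined protocol and SAP*

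**What the plan says.** Section 13.3, repeated in the Synopsis under Efficacy Analysis, takes the worse eye for each lens set and forms the VisionCheck-minus-phoropter difference in LogMAR. On reporting it says: "The mean, SD, and two-sided 95% confidence interval (CI) will be reported across all subjects for worst eye, OD, OS, and OU". The same sentence then sets the decision on another limit: "if the upper bound (one sided 95% CI) does not include the value 0.1 for the worst eye comparison, then non-inferiority will be declared".

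The rule is repeated for the autorefractor, and then again by age: "Analyses will be repeated for each age stratum including ages 30 through 65 and ages 45 through 65". Section 7.3.1 makes these endpoints in their own right. The primary is the phoropter comparison at ages 45 through 65. The secondary non-inferiority endpoints are the phoropter comparison at 30 through 65 and the autorefractor comparison "analyzed with age strata 30 through 65 years and 45 through 65 years". That gives one primary and three secondary declarations.

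Neither Section 13.3 nor the Synopsis gives a testing order, splits alpha, or says whether a secondary claim depends on the primary.

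**The concern.** There are two separate issues.

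- **Display and decision.** A one-sided 95% upper bound is the upper limit of a two-sided 90% CI. It lies below the upper limit of the two-sided 95% CI that the report will carry. For some results the reader would see an interval containing 0.1 next to a statement that non-inferiority was shown, and the number behind that statement would not be among the listed outputs.
- **Four declarations, one rule.** Section 5 gives the study's intent as non-inferiority to both comparators, so the secondary claims are likely to be quoted as results. As written, a study that fails against the phoropter at 45 through 65 could still declare non-inferiority for the wider age range or for the autorefractor, each at a fresh 5%.

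**Working it through.** **Inputs**

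- Margin: Section 7.4, "A statistical non-inferiority margin of 0.1 LogMAR has been chosen because the one-line ETDRS difference is an acceptable boundary for corrected visual acuity".
- Subjects: at least 100 evaluable (Section 13.1), about 65% aged 45 through 65 (Section 7.2). This gives 0.65 × 100 = 65 in the primary stratum, assuming the enrolment split carries over to evaluable subjects.
- SD: 0.077 (Section 13.1). The values 0.154 (2 × 0.077) and 0.20 are assumptions, used because Section 13.1 allows for a larger SD than planned.
- Correlation between the phoropter and autorefractor differences: not in the documents; assumed 0.3 to 0.9.

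**Step 1: the plan's own figure.** For margins of 0.1 and 0.05, Section 13.1 says the trial "would require approximately 10 and 40 subjects, respectively, with 90% power on the BCVA from the resulting lens from each approach", and adds "This assumes the devices are roughly equivalent and the standard deviation (SD) is 0.077". It states no alpha. Take n = 2 × [SD × (z(1−α) + z(0.90)) / margin]².

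- One-sided 0.05: 2 × [0.077 × (1.645 + 1.282) / 0.1]² = 10.2 for margin 0.1, and 40.6 for margin 0.05.
- One-sided 0.025: 12.5 and 49.8, rounded up to 13 and 50.
- Without the factor 2: 5.1 and 20.3 at 0.05; 6.2 and 24.9 at 0.025. A paired t calculation gives 7 and 22, or 9 and 27.

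Of the variants tried, only one-sided 0.05 in the first form gives about 10 and 40. The sample size therefore agrees with the decision rule. (The factor 2 belongs to a two-sample comparison, whereas the analysis is within subject. That is a separate matter and does not affect this point.)

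**Step 2: the two limits.** A result passes if the observed mean is below 0.1 − t × SD/√n. At n = 65 and SD 0.077, the standard error is 0.077/√65 = 0.00955.

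| SD | Passes one-sided 95% bound below | Two-sided 95% CI excludes 0.1 below |
|---|---|---|
| 0.077 | 0.1 − 0.0159 = 0.0841 | 0.1 − 0.0191 = 0.0809 |
| 0.20 (assumed) | 0.1 − 0.0414 = 0.0586 | 0.1 − 0.0496 = 0.0504 |

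Between the two columns, the declaration and the displayed CI disagree.

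**Step 3: chance of landing in that band.** This is the power under the one-sided rule minus the power under the two-sided limit (noncentral t, n = 65).

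- True difference 0: below 0.001% at SD 0.077; 99.04% − 97.78% = 1.26% at SD 0.20.
- True difference 0.05 (assumed): 99.98% − 99.93% = 0.05% at SD 0.077; 82.77% − 73.18% = 9.59% at SD 0.154; 63.66% − 51.01% = 12.65% at SD 0.20.
- True difference exactly 0.1: 5% − 2.5% = 2.5%.

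**Step 4: four declarations.** The sum of the four levels is 4 × 0.05 = 0.20, and independence would give 1 − 0.95⁴ = 0.185. Both overstate the risk, because the 65 subjects are nested in the 100 and both comparisons use the same VisionCheck scores. The table shows 100,000 simulated trials per row, with normal differences and all four true differences at 0.1.

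| Assumed correlation | Any false declaration | Primary falsely declared | False secondary, primary failed |
|---|---|---|---|
| 0.3 | 13.62% | 4.95% | 8.67% |
| 0.5 | 13.11% | 5.11% | 8.00% |
| 0.7 | 11.66% | 4.86% | 6.80% |
| 0.9 | 10.18% | 5.06% | 5.11% |

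The last two columns add up to the second, within rounding. Simulation error is about √(0.13 × 0.87 / 100,000) = 0.1 percentage point. Using one-sided 0.025 with no testing order still gives any-false-declaration rates of 7.4%, 7.1%, 6.2% and 5.5% down the rows, so a stricter level alone does not remove the multiplicity.

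**The case against.** The defence has force on both halves.

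- **Sidedness.** The one-sided 95% bound is written into the decision rule, and the stated sample sizes agree with it, so it looks deliberate. A reader might infer that the trial should run at 2.5% and has doubled its error by mistake. The documents do not support that: they nowhere adopt 2.5%, and the two-sided 95% CI is a reporting item that is also given for OD, OS and OU, which carry no decision. Under the plan's own assumptions (no true difference, SD 0.077), the display and the decision would almost never disagree. What stands is that the number driving the decision is not among the listed outputs, and that the chance of disagreement grows if the SD and the true difference are both larger than planned.
- **Multiplicity.** A reader might also infer that the primary's error is inflated, or that a secondary success can rescue a failed primary. Neither follows. Sections 6.1, 6.2 and 7.3.1 name a single primary and label the rest secondary, its error stays at 5%, and no text lets a secondary result replace it. The 10% to 14% covers primary and secondary claims together, a family the plan does not say it controls, and it assumes the least favourable truth. What stands is that Section 13.3 applies the same declaration rule to the secondary comparisons, without saying that they are descriptive or conditional on the primary.

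**Conclusion.** The point holds in limited form. The plan's 5% one-sided level is prespecified and consistent with its sample size; what is missing is a report of the bound that decides. The practical effect of that is small: a band of about 0.003 LogMAR at SD 0.077 and about 0.008 at an assumed SD of 0.20, both at n = 65.

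The weightier part is the absence of any testing order for the three secondary declarations. In the worst case they raise the chance of some false non-inferiority statement from 5% to about 10% to 14%, of which about 5 to 9 percentage points are secondary statements made after the primary has failed. These figures rest on the assumed correlation range of 0.9 to 0.3, on 65 of 100 evaluable subjects being in the primary stratum, and on all true differences lying at the margin. They fall if the true differences are worse than 0.1.

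**What to change.** 1. **Fix the testing order.** State in Section 13.3 and the Synopsis that the four claims are tested in a prespecified sequence, each at the one-sided 5% level, starting with the phoropter at ages 45 through 65. The sponsor should set the order of the three secondary claims before analysis. Testing stops at the first failure, and every later comparison is descriptive. This holds the chance of any false declaration at 5%, adds no subjects and leaves the primary untouched. The cost is that an early failure blocks all later secondary claims, including any that would have passed alone.
2. **Report what decides.** Add the one-sided 95% upper bound (equivalently the two-sided 90% CI) next to the two-sided 95% CI for each worst-eye comparison, and say which limit the declaration uses. This costs only wording and one more table column.
3. **Optional: decide on the two-sided 95% limit (one-sided 0.025).** Display and decision would then coincide, but this is a trade-off. By the plan's formula the stated 10 and 40 subjects become about 13 and 50, so Section 13.1 and the Synopsis would need revising. At n = 65, power falls from 99.0% to 97.8% with no true difference and an assumed SD of 0.20. It falls from 82.8% to 73.2% with an assumed true difference of 0.05 and SD of 0.154. If the sponsor keeps one-sided 5%, a sentence giving the reason is enough.

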13.4. Safety Analyses

13.4.1. Adverse Events

Adverse events, ADEs, UADEs, and SAEs will be reported with counts and percentages. Adverse events that can be associated with a particular device will be reported separately from those without clear attribution. Adverse events will be coded using MedDRA terminology. A subject experiencing more than 1 instance of an event will be counted only once for that event. Analyses will be repeated for each age stratum including ages 30 through 65 and ages 45 through 65. Unanticipated ADEs will be flagged in the by-subject listings of all AEs.

14. DIRECT ACCESS TO SOURCE DATA/DOCUMENTS

The investigator/institution shall provide direct access to source data/documents for study-related monitoring, audits, IRB review, and regulatory inspection.

14.1. Study Monitoring

According to ICH Good Clinical Practice (GCP) guidelines, the sponsor of the study is responsible for ensuring the proper conduct of the study with regard to protocol adherence and validity of data recorded on the eCRFs. The sponsor or its designee is responsible for assigning the study monitor(s) to this study.

The investigator shall permit the study monitor to review study data as frequently as deemed necessary to ensure that data are being recorded in an adequate manner and that protocol adherence is satisfactory.

The investigator shall access medical records for the study monitor so that entries in the eCRFs may be verified. The investigator, as part of his/her responsibilities, is expected to cooperate with the sponsor or designee in ensuring that the study adheres to GCP requirements.

The investigator may not recruit subjects into the study until such time that a site visit has been made by an EyeQue or designee monitor to conduct a detailed review of the protocol and eCRF and study instructions.

14.2. Audits and Inspections

Authorized representatives of EyeQue, a regulatory authority, an IRB or an IEC may visit the site to perform audits or inspections, including source data verification. The purpose of an EyeQue audit or inspection is to systematically and independently examine all study-related activities and documents to determine whether these activities were conducted, and data were recorded, analyzed, and accurately reported according to the protocol, ICH GCP guidelines, and any applicable regulatory requirements. The investigator should contact EyeQue immediately if contacted by a regulatory agency about an inspection.

14.3. Institutional Review Board/Independent Ethics Committee

Prior to the start of the study, the investigator is responsible for ensuring that the protocol and informed consent form (ICF) have been reviewed and approved by a relevant IRB/IEC. The IRB/IEC shall be appropriately constituted and perform its functions in accordance with FDA, ICH GCP, and local requirements as applicable.

The IRB shall approve all protocol amendments (except for logistical or administrative changes), written ICFs and documents updates, subject recruitment procedures (e.g. advertisements), written information to be provided to the subjects, available safety information, information about payment and compensation available to subjects, the investigator's curriculum vitae and/or other evidence of qualifications and any other documents requested by the IRB and regulatory authority (competent authority) as applicable.

When required, the IRB and regulatory authority must be notified of completion or termination of this study, and sent a copy of the study synopsis in accordance with necessary timelines.

15. QUALITY CONTROL AND QUALITY ASSURANCE

The sponsor will implement and maintain quality control procedures to ensure that this study is conducted and data are generated, documented, and reported in compliance with the protocol, and applicable regulatory requirements.

The sponsor or designee will routinely conduct monitoring and/or auditing visits to the study site to verify the adherence to the study protocol, the protection of the rights and well-being of the subjects; and the accuracy and completeness of reported study data recorded on the source documentation. A suitable qualified representative will monitor the clinical investigation as follows:

- Conduct pre-study evaluation visits to verify site qualifications.
- Conduct site initiation visit after IRB/IEC approval and at or before first subject visit.
- Conduct periodic monitoring visits.
- Compare eCRFs to source documents for accuracy, completeness, legibility, and logic.
- Review investigator's files for accuracy, currency, and completeness.
- Conduct ongoing review of site for continued ability to conduct the study.
- Ensure that informed consents are obtained.
- Ensure that IRB/IEC review is current.
- Ensure protocol compliance and document any deviations or violations.
- Assure untoward effects are reported.
- Conduct closeout visit after all subject visits are complete and data in eCRFs are confirmed.
- Follow-up with all ongoing issues, as necessary.
- Prepare reports of visits.

16. ETHICS

16.1. Ethics Review

The protocol and supporting documents for this study will be reviewed and approved by an appropriately constituted IRB/IEC prior to study initiation. The investigator will not start this study before providing EyeQue with evidence of IRB approval.

The investigator will promptly report to the IRB all changes in the research activity and all unanticipated problems involving risks to subjects. The investigator will not make any changes in the research without IRB approval, except where necessary to eliminate apparent immediate hazards to the subjects.

The investigator is responsible for informing the IRB of any amendment to the protocol in accordance with local requirements. In addition, the IRB or IEC must approve all advertising used to recruit patients for the study. The protocol must be re-approved by the IRB or IEC upon receipt of amendments and annually, as local regulations require.

A progress report will be submitted by the investigator to the IRB or IEC at intervals specified by the IRB/IEC, but not less than annually. A copy of this progress report will be sent to EyeQue. After completion of the study, the investigator will submit a final report to the IRB/IEC.

16.2. Ethical Conduct of the Study

The study will be conducted in accordance with GCP as contained in the US CFR governing the protection of human subjects (Title 21, Part 50).

EyeQue is responsible for the ongoing safety evaluation of the product and will expedite the notification of all participating investigators and regulatory authorities of findings that are reportable, or could alter the IRB/IEC approval to continue the study.

16.3. Written Informed Consent

The investigator will ensure that written informed consent is obtained from each participant in accordance with applicable regulations.

Subjects will be interviewed at the initial screening visit by qualified staff at the site and will be provided with a full description of the nature and purpose of the study. The subject will be given adequate time to consider the risks and benefits associated with participation in the study. Each subject will provide written informed consent prior to participating in any study procedures. The original signed consent forms will be retained on file at the clinical site and a copy will be given to the subject. Case histories (subject charts) will also document that informed consent was obtained prior to the subject's participation in the study.

16.4. Authorization to Disclose Protected Health Information

If required under Health Insurance Portability and Accountability Act regulations, or other applicable regulations subjects will be informed of the following information:

Version 3.0 (17 June 2019)

- the sponsor of the study;
- any contractors that may be involved in the study;
- the purpose of the protected health information (PHI) being collected;
- the possibility that the PHI may be re-disclosed;
- the duration of the authorization;
- the subject's rights to revoke the authorization; and,
- the right of the subject to refuse signature and limit access to PHI during the conduct of the study (US 21 CFR Title 45, Parts 160 and 164).

Authorization to disclose PHI must be obtained before the subject enters the study.

